### **Follow-up period**

[figure not shown]
The follow-up period is 12 weeks with the last follow-up visit (Week 36) corresponding to 16 weeks after the last treatment dose. No study treatment will be given during the post-treatment follow-up period. Participants will continue with the background medication and will be allowed to take their rescue medication on an as needed basis. [REDACTED]

[REDACTED] Participants will be required to visit the study center every 4 weeks during post-treatment / follow-up period.

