## **Women of child-bearing potential**

Women of child-bearing potential must be informed that taking the study treatment may involve unknown risks to the fetus if pregnancy were to occur during the study, and agree that in order to participate in the study they must adhere to the contraception requirements outlined in the exclusion criteria. If there is any question that the participant will not reliably comply, they should not be entered or continue in the study.

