24. History of long QT syndrome or whose QTcF (Fridericia) measured at screening visit (Visit 1) is prolonged (> 450 ms for males or > 460 ms for females).
25. Pregnant or nursing (lactating) women.
26. Female participants, including adolescent females of 12 to less than 18 years of age, of child-bearing potential, defined as all women physiologically capable of becoming pregnant, unless they are using effective methods of contraception during dosing of study treatment. Effective contraception methods include:
  - Total abstinence (when this is in line with the preferred and usual lifestyle of the participant. Periodic abstinence (e.g., calendar, ovulation, symptothermal, post-ovulation methods) and withdrawal are not acceptable effective methods of contraception
  - Female sterilization (have had surgical bilateral oophorectomy with or without hysterectomy), total hysterectomy or bilateral tubal ligation at least six weeks before

taking study treatment. In case of oophorectomy alone, only when the reproductive status of the woman has been confirmed by follow up hormone level assessment

- Male sterilization (at least 6 months prior to screening). For female participants on the study, the vasectomized male partner should be the sole partner for that participant
- Barrier methods of contraception: Condom or Occlusive cap (diaphragm or cervical/vault caps). For UK: with spermicidal foam/gel/film/cream/ vaginal suppository
- Use of oral, (estrogen and progesterone), injected or implanted hormonal methods of contraception or other forms of hormonal contraception that have comparable efficacy (failure rate <1%), for example hormone vaginal ring or transdermal hormone contraception or placement of an intrauterine device (IUD) or intrauterine system (IUS)

In case of use of oral contraception women should have been stable on the same pill for a minimum of 3 months before taking study treatment.

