Women are considered post-menopausal if they have had 12 months of natural (spontaneous) amenorrhea with an appropriate clinical profile (e.g. age appropriate, history of vasomotor symptoms). Women are considered not of child bearing potential if they are post-menopausal or have had surgical bilateral oophorectomy (with or without hysterectomy), total hysterectomy or tubal ligation at least six weeks ago. In the case of oophorectomy alone, only when the reproductive status of the woman has been confirmed by follow up hormone level assessment is she considered not of child bearing potential.

If local regulations deviate from the contraception methods listed above to prevent pregnancy, local regulations apply and will be described in the ICF.

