### 6.1.5 Treatment duration

The planned duration of treatment is 24 weeks, with the last planned dispensing visit for every participant at week 20. Discontinuation of the study drug treatment can be initiated by either the participant or the investigator ([Section 9.1.1](#)).

Participants who complete participation in this trial prior to the investigational treatment becoming available in the country of the participant and continues to derive clinical benefit from the treatment based on the investigator's evaluation may receive post-trial access. Post Trial Access (PTA) means the provision of treatment to trial participants following their completion of trial participation. PTA will be provided until one of the following is met: participant no longer derives clinical benefit, investigator discontinues treatment, launch or

reimbursement (where applicable), treatment fails to achieve registration in the trial participant’s country, or the clinical program is discontinued for any other reason.

Mechanisms for provision of PTA may include an extension phase to this study, a separate extension protocol, a rollover protocol, a registry trial, provision of the Novartis investigational product in a non-trial setting (known as post-study drug supply (PSDS)) when no further safety or efficacy data are required, or any other mechanism appropriate for the country.

The PTA mechanism must comply with local laws and regulations in the participating trial countries. If Novartis discontinues the PTA for this trial, Novartis will work with investigators to transition patients onto locally available alternative treatment, or standard of care.

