Information about common side effects already known about the investigational drug can be found in the Investigator's Brochure (IB). This information will be included in the participant informed consent and should be discussed with the participant during the study as needed. Any new information regarding the safety profile of the investigational drug that is identified between IB updates will be communicated as appropriate, for example, via an investigator notification or an aggregate safety finding. New information might require an update to the informed consent and then must be discussed with the participant.

The following informed consents are included in this study:

■ [REDACTED]

- A subsection that requires a separate signature for the 'Optional exit interview'
- A subsection that requires a separate signature for additional research

■ [REDACTED]

- Adult Pregnancy Follow-up Consent for pregnant participants
- Parent/legal guardian informed consent for adolescent participants which includes:
  - A subsection that requires a separate signature for additional research
- Adolescent assent form
- Parent/legal guardian informed consent for pregnancy follow up for adolescent participants

■ [REDACTED]

Women of child bearing potential must be informed that taking the study treatment may involve unknown risks to the fetus if pregnancy were to occur during the study and agree that in order to participate in the study they must adhere to the contraception requirements.

Declining to participate in the optional assessments ( [REDACTED] exit interviews, [REDACTED] pregnancy outcomes reporting and additional research) will in no way affect the participant's ability to participate in the main research study.

A copy of the approved version of all consent forms must be provided to Novartis after IRB/IEC approval.

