2.4 Treatments (study treatment, rescue medication, concomitant therapies, compliance)

2.4.1 Study treatment / compliance

The analysis of treatment will be performed by each treatment group based on the SAF in each cohort separately.

The number of participants and the duration of exposure to each study drug and dose will be summarized by treatment. Duration of exposure is defined as the date of the last treatment minus the date of first study drug administration plus 4 weeks (28 days).

In addition, the number of doses will be presented. A partial dose will be considered as if 100% of the dose of the assigned treatment has been administered.

For all protocol deviations (PDs) listings will be generated by PD category and treatment groups in each cohort separately.

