2.7.1.1 Exposure-Adjusted Incidence Rate

Due to expected differences in exposure and follow-up due to varied duration of study participation between participants, adverse event incidence rates will be provided as “exposure adjusted AE incidence rates”.

The EAIR is defined as the number of subjects with a specific event divided by the total exposure-time among the subjects in the study group. That is, the EAIR is calculated as:

$EAIR = n / \sum t_i$, where n is the number of subjects having the i^{th} type event, and t_i is a subject's exposure time and defined as the shortest of the following:

- 1) time to the first episode of the i^{th} type event (if the event occurs),
- 2) duration of study treatment plus the 16-week washout period (approximately corresponding to five half-lives) after last treatment dose, or
- 3) end of the analysis period (Week 12 for the placebo period, week 36 for all safety follow-up).

The total exposure time of all subjects in a treatment group is $\sum t_i$. The EAIR is interpreted as the number of events occurring in a population per unit time. The exact Poisson 95% confidence interval for the EAIR will be provided as well, where an exact $100*(1-\alpha)\%$ confidence interval will be derived as follows (Garwood 1936, Sahai and Khurshid 1993):

- Lower confidence limit $L = \frac{0.5C_{\alpha/2,2n}}{\sum t_i}$ for $n>0$, 0 otherwise,
- Upper confidence limit $U = \frac{0.5C_{1-\alpha/2,2n+2}}{\sum t_i}$,

where $C_{\alpha,k}$ is the α th quantile of the Chi-square distribution with k degrees of freedom.

Whenever applicable, exposure adjusted incidence rates will be provided for the type as below:

1. TEAE and TESAE: Primary SOC level, PT level
2. Most frequent (at least 5% in any treatment group) TEAE: Primary SOC level, PT level

Treatment emergent AE of special interest.

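### Criterion 26 requires contraception only while study drug is being dosed, leaving the 12-week follow-up (Weeks 24 to 36) with no contraception requirement and no stated reason

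*Protocol*

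**What the plan says.** Protocol section 5.2, criterion 26, excludes women of child-bearing potential, including adolescents, "unless they are using effective methods of contraception during dosing of study treatment". It then lists acceptable methods. It gives no period after the last dose.

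The other places that touch on contraception add no duration:

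- Section 4.5 (Women of child-bearing potential) says that "taking the study treatment may involve unknown risks to the fetus if pregnancy were to occur during the study", and refers back to the exclusion criteria for what is required.
- Section 7 says that "in order to participate in the study they must adhere to the contraception requirements", without a time limit.
- The local-rule clause at the end of section 5.2 reads "If local regulations deviate from the contraception methods listed above to prevent pregnancy, local regulations apply". It concerns methods, not how long they are used.

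On timing, section 6.1.5 states: "The planned duration of treatment is 24 weeks, with the last planned dispensing visit for every participant at week 20". Section 3.1 states: "The follow-up period is 12 weeks with the last follow-up visit (Week 36) corresponding to 16 weeks after the last treatment dose". Table 4-1 says the follow-up length was chosen partly from the drug's half-life. SAP section 2.7.1.1 limits a subject's exposure time for adverse event rates to, among other bounds, "duration of study treatment plus the 16-week washout period (approximately corresponding to five half-lives) after last treatment dose".

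**The concern.** A woman who follows criterion 26 to the letter may stop contraception when dosing ends. By the plan's own washout figure, drug is still being eliminated then and for most of follow-up. The plan treats those weeks as drug-relevant for other purposes: treatment-emergent adverse events are counted up to 16 weeks after the last dose (Protocol section 12.5.2, SAP section 2.7.1), and urine pregnancy tests continue through follow-up (Protocol section 8.4.3). Prevention of pregnancy is the one element that stops with dosing.

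At stake is avoidable fetal exposure to an antibody whose fetal risk the protocol calls unknown. The gap applies to adolescents and to anyone who stops treatment early. It has no bearing on sample size, power or type I error.

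**Working it through.** **Inputs from the documents**

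- Last injection: Week 20 (Protocol 6.1.5).
- End of treatment: Week 24. End of study: Week 36 (Protocol 3.1, Table 8-1).
- Discontinuation visit for early stoppers: 4 weeks after the last dose (Protocol 9.1.1).
- Washout: 16 weeks, approximately five half-lives (SAP 2.7.1.1).

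**Plan's own figures.** Follow-up is 36 − 24 = 12 weeks, and Week 36 falls 36 − 20 = 16 weeks after the last dose. Both match Protocol section 3.1.

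**Length of the gap.** The protocol does not define when dosing ends.

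- Main reading, Week 24. This fits the 24-week treatment duration and the SAP exposure rule (SAP 2.4.1), which adds 28 days to the last dose. Gap: 12 weeks = 84 days; 12/36 = 33% of the time from randomization to Week 36.
- Literal reading, Week 20. Gap: 16 weeks = 112 days; 16/36 = 44%.
- Early stoppers, with dosing taken to end at the discontinuation visit: 16 − 4 = 12 of the 16 washout weeks are uncovered.

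**How much drug remains.** The documents give no half-life. I assume first-order decline with k half-lives in 16 weeks and ignore absorption. Because the SAP says approximately five, I take k = 5 with a range of 4 to 6.

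- Half-life = 112/k days.
- Fraction of the level after the Week 20 dose remaining t weeks later = 2^(−k·t/16).
- Share of all exposure after the last injection (area under the curve) that falls in Weeks 24 to 36 = 2^(−4k/16) − 2^(−k).

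| | k = 4 | k = 5 | k = 6 |
|---|---|---|---|
| Half-life (days) | 28.0 | 22.4 | 18.7 |
| Remaining at Week 24 (t = 4) | 50% | 42% | 35% |
| Remaining at Week 36 (t = 16) | 6.3% | 3.1% | 1.6% |
| Share of exposure in Weeks 24 to 36 | 44% | 39% | 34% |

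On these assumptions, roughly two fifths of the exposure after the last injection falls in weeks when the protocol asks for no contraception. By Week 36 little drug is left, so a 16-week period would cover nearly all of it.

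**The case against.** The strongest objection is that the need for a post-dose period depends on reproductive-toxicity data, which would sit in the Investigator's Brochure. Neither the Brochure nor the consent form is available here, and either could state or justify a period. The five-half-life figure was written for adverse event person-time. The comparable rule in criterion 1 governs washout of other investigational drugs and is only one limb of that rule. Neither defines a fetal-risk window. The percentages rest on an inferred half-life and show only that an antibody persists.

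All of this stands. It limits the point to a low-cost safety improvement and means no error has been proven. It does not remove the gap: the protocol sets a rule, the rule stops at dosing, and no reason is given. The proposed wording leaves the sponsor free to justify a shorter period.

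The protocol does have safeguards. Urine pregnancy tests run through follow-up, pregnancies must be reported within 24 hours, and section 4.5 says women who may not comply reliably should not enter or continue. The tests and reports act only after conception, and in follow-up there is no treatment left to stop. The compliance sentence adds no duration to what must be complied with.

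The trial was also terminated early, with 39 participants enrolled (SAP section 1.1). That limits the practical effect now. It also moved everyone then on treatment into follow-up, which is the period left uncovered.

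**Conclusion.** The concern holds. As written, criterion 26 leaves 12 weeks after treatment (Weeks 24 to 36), or 16 weeks on the literal reading, without required contraception. Nothing visible in the protocol or SAP fills or explains the gap, which sits badly with the protocol's own warning of unknown fetal risk throughout the study.

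The length of the gap follows from the visit schedule and depends only on when dosing is taken to end. The residual-drug figures also depend on the SAP's approximate washout statement and on first-order decline. Confidence is medium, because the fetal-risk data are not visible. The change should be made in the plan as written or if it is reused.

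**What to change.** Amend criterion 26 to require effective contraception during dosing and for 16 weeks after the last dose of study treatment. That is Week 36 for completers, and the same 16 weeks from the last dose for participants who stop early. If the sponsor considers a shorter period safe, state it and cite the supporting data. Carry the same period into sections 4.5 and 7.

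The cost is a wording amendment and a contraception commitment 12 weeks longer (16 on the literal reading). Because treatment is blinded, it also binds placebo participants who stop before Week 12 and never receive ligelizumab. No visits or tests are added, since pregnancy testing already runs through follow-up. Adherence could not be checked in women who withdraw consent, and could be checked only by telephone in those who decline visits.

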## 6 Treatment

### 6.1 Study treatment

Study treatment includes investigational drug and placebo. Novartis Global Clinical Supply (GCS) will provide these investigational products in an open-label fashion. Unblinded pharmacists are responsible at sites towards IMP accountability.

#### 6.1.1 Investigational and control drugs

**Table 6-1 Investigational and control drug**

Investigational/ Control Drug (Name and Strength)	Pharmaceutical Dosage Form	Route of Administration	Presentation	Sponsor (global or local)
Ligelizumab 120 mg per 1 mL	Liquid in vial (solution for injection)	s.c	Open label kits; vials	Novartis Pharma AG
Ligelizumab Placebo 0 mg per 1 mL	Liquid in vial (solution for injection)	s.c	Open label kits; vials	Novartis Pharma AG

For 72 mg arm, 0.6 mL of 1mg/mL solution will be administered

### 6.1.2 Additional study treatments

No other treatment beyond investigational drug (ligelizumab) and control drug (placebo to ligelizumab) are included in this trial. Participants will continue to use their background medication H1-AH (at local-approved doses) with a stable regimen during the study. For rescue medication, see [Section 6.2.3](#).

### 6.1.3 Supply of study treatment

Novartis Global Clinical Supply (GCS) will supply the investigational drug and the placebo. GCS will not supply other treatment that are listed in [Section 6.2](#).

### 6.1.4 Treatment arms/group

Participants in the symptomatic dermographism and cold urticaria cohorts will be assigned at Week 0 to one of the following 4 treatment arms in a ratio of 2:2:1:1. Each participant will receive 1 injection every 4 weeks at the clinic:

- Ligelizumab 120 mg arm: 1 injection of 1.0 mL ligelizumab
- Ligelizumab 72 mg arm: 1 injection of 0.6 mL ligelizumab
- Placebo / ligelizumab 120 mg arm: 1 injection of 1.0 mL ligelizumab placebo from Week 0 through Week 8; 1 injection of 1.0 mL ligelizumab from Week 12 through Week 20
- Placebo / ligelizumab 72 mg arm: 1 injection of 0.6 mL ligelizumab placebo from Week 0 through Week 8; 1 injection of 0.6 mL ligelizumab from Week 12 through Week 20

Participants in the cholinergic urticaria cohort will be assigned at Week 0 to one of the following 2 treatment arms in a ratio of 1:1. Each participant will receive 1 injection every 4 weeks:

- Ligelizumab 120 mg arm: 1 injection of 1.0 mL ligelizumab
- Placebo / ligelizumab arm: 1 injection of 1.0 mL ligelizumab placebo from Week 0 through Week 8; 1 injection of 1.0 mL ligelizumab from Week 12 through Week 20

During the double-blind treatment period, study drug will be administered at 6 visits as per [Table 6-3](#) and [Table 8-1](#). Due to the specifics of the blinding procedure in this trial, the dispensing and administration of the study treatments must be performed by suitable authorized site personnel who are otherwise not involved in study conduct. Further details are provided in [Section 6.3.2](#), [Section 6.4](#) and [Section 6.7](#). All study treatment dispensing visits will occur at the clinic.

### 6.1.5 Treatment duration

The planned duration of treatment is 24 weeks, with the last planned dispensing visit for every participant at week 20. Discontinuation of the study drug treatment can be initiated by either the participant or the investigator ([Section 9.1.1](#)).

Participants who complete participation in this trial prior to the investigational treatment becoming available in the country of the participant and continues to derive clinical benefit from the treatment based on the investigator's evaluation may receive post-trial access. Post Trial Access (PTA) means the provision of treatment to trial participants following their completion of trial participation. PTA will be provided until one of the following is met: participant no longer derives clinical benefit, investigator discontinues treatment, launch or

reimbursement (where applicable), treatment fails to achieve registration in the trial participant’s country, or the clinical program is discontinued for any other reason.

Mechanisms for provision of PTA may include an extension phase to this study, a separate extension protocol, a rollover protocol, a registry trial, provision of the Novartis investigational product in a non-trial setting (known as post-study drug supply (PSDS)) when no further safety or efficacy data are required, or any other mechanism appropriate for the country.

The PTA mechanism must comply with local laws and regulations in the participating trial countries. If Novartis discontinues the PTA for this trial, Novartis will work with investigators to transition patients onto locally available alternative treatment, or standard of care.

## 6.2 Other treatment(s)

### 6.2.1 Concomitant therapy

This study requires concurrent use of one second generation H1-AH at local approved doses as background medication. Participants must remain on a stable treatment regimen (type and dose of H1-AH) throughout the study. If a participant must switch to another background H1-AH (at approved dose) as a result of an AE or it being no longer available in the country, the participant will be considered to have remained on stable treatment.

All medications, procedures, and significant non-drug therapies (including physical therapy and blood transfusions) administered after the participant was enrolled into the study must be recorded on the appropriate Case Report Forms.

Each concomitant drug must be individually assessed against all exclusion criteria/prohibited medication. If in doubt, the investigator should contact the Novartis medical monitor before randomizing a participant or allowing a new medication to be started. If the participant is already enrolled, contact Novartis to determine if the participant should continue participation in the study.

### 6.2.2 Prohibited medication

Use of the class of treatments displayed in [Table 6-2](#) is NOT allowed after start of screening (Visit 1) and up until after the end of the follow-up period. The minimum required period without prohibited treatment before screening visit (Visit 1) is also listed in [Table 6-2](#). Each concomitant drug must be individually assessed against all exclusion criteria and the table below to see if it is allowed. If in doubt, the investigator should contact Novartis or delegate before randomizing a participant or allowing a new medication to be started.

**Table 6-2 Prohibited medication**

Medication	Prohibition period prior to Screening visit (Visit 1)	Action taken if prohibited medication is administered
Omalizumab	No prior use allowed	Discontinue from study
Ligelizumab	No prior use allowed	Discontinue from study
Routine (daily or every other day during more than one consecutive day /month) doses of systemic corticosteroids*	30 days prior to Visit 1	Stop prohibited treatment

Medication	Prohibition period prior to Screening visit (Visit 1)	Action taken if prohibited medication is administered
IV/IM/IA corticosteroids	30 days prior to Visit 1	Stop prohibited treatment or discontinue from study treatment
Beta-blocker therapy	7 days prior to Visit 1	Stop prohibited treatment or discontinue from study treatment
Leukotriene antagonists	Stop at Visit 1	Stop prohibited treatment or discontinue from study treatment
H2-antihistamines	Stop at Visit 1	Stop prohibited treatment or discontinue from study treatment
First generation H1-antihistamines	Stop at Visit 1	Stop prohibited treatment or discontinue from study treatment
Hydroxychloroquine or chloroquine	30 days prior to Visit 1	Stop prohibited treatment or discontinue from study treatment
Other immunosuppressive and immunomodulatory medication with or without known effect on CINDU including but not limited to Methotrexate, cyclosporine A, cyclophosphamide, tacrolimus and mycophenolate mofetil, anti-IL-1, anti-TNF-alpha	30 days prior to Visit 1	Stop prohibited treatment or discontinue from study treatment
Intravenous immunoglobulin G	30 days prior to Visit 1	Discontinue study treatment
Plasmapheresis	30 days prior to Visit 1	Discontinue study treatment
Regular (daily or every other day) doxepin (oral)	14 days prior to Visit 1	Stop prohibited treatment or discontinue from study treatment
Vaccination with inactivated viruses	48 hours prior to each dosing visit (i.e. Week 0 to Week 20)	Stop prohibited treatment
Live attenuated vaccine	30 days prior to Visit 1	Discontinue study treatment

\*Corticosteroids (CS) with limited systemic exposure for non-CINDU indications can be used (e.g. Intra nasal or any topical CS) on an as-needed basis.

If the prohibited treatment was used during the study for any indication, the participant must discontinue use of the prohibited treatment if the participant wishes to continue in the study. If the participant must continue a prohibited medication during the study, the participant must discontinue study treatment. If the participant receives a live virus vaccination during the study, the participant must discontinue study treatment.

Table 6-2 is not considered all inclusive. Medication should be assessed for adherence to the indication and other inclusion/exclusion criteria.

